10 PHARMACOVIGILANCE

10.1 Definitions

Term	Definition
Adverse Event (AE)	Any untoward medical occurrence in a participant to whom a medicinal product has been administered, including occurrences which are not necessarily caused by or related to that product.
Adverse Reaction (AR)	An untoward or unintended response in a participant to an investigational medicinal product which is related to any dose administered to that participant.

	The phrase "response to an investigational medicinal product" means that a causal relationship between a trial medication and an AE is at least a reasonable possibility i.e. the relationship cannot be ruled out.
	All cases judged by either the reporting medically qualified professional or the Sponsor as having a reasonable suspected causal relationship to the trial medication qualify as adverse reactions
Reference Safety	The RSI is a list of medical terms detailing the ARs that are expected for an
Information (RSI)	IMP and must be referred to when assessing a SAR for expectedness.
Serious Adverse Event (SAE)	 A serious adverse event is any untoward medical occurrence that: Results in death Is life-threatening* Requires inpatient hospitalisation or prolongation of existing hospitalisation Results in persistent or significant disability/incapacity Consists of a congenital anomaly or birth defect Other important medical events that jeopardise the participant or require intervention to prevent one of the above consequences * - life-threatening refers to an event in which the participant was at immediate risk of death at the time of the event; it does not refer to an event which hypothetically might have caused death if it were more severe.
Serious Adverse Reaction (SAR)	An adverse event that is both serious and, in the opinion of the reporting investigator, believed with reasonable probability to be due to one of the trial treatments, based upon the information provided.
Suspected Unexpected Serious Adverse Reaction (SUSAR)	A serious adverse reaction, the nature and severity of which is not consistent with the approved Reference Safety Information.

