4.2 Analysis populations

There will be two analysis populations:

1. Participants who have completed the baseline observation period and have received at least one dose of CBZ.

2. Participants who have completed their baseline observation period and have been prescribed, on average, at least 15 mg/kg of CBZ over their first 12 -months of treatment, i.e. a dose which is at least 75% of the dose recommended from Stage 1. Note that some participants will have longer than 12 months of treatment.

Adverse events will be reported for all participants who start their baseline period.

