4.4.3 Additional secondary analyses

Use of surgical interventions to manage the condition will be captured on the eCRF over the whole follow up period. These will be reported descriptively as the type and proportion of participants experiencing an event per three month period from baseline until the end of trial follow up.

5 Safety

Laboratory safety assessments outside the appropriate local normal reference range will be reported at a participant level. Abnormal physical examinations will be reported at a participant level together with any further details provided.

All AEs occurring from the point of consent to the end of trial participation are recorded in the trial MACRO database eCRF. AEs are assessed for their relationship to treatment and coded as: Unrelated, Unlikely, Possible, Probable, Definitely, or Not assessable. Severity is graded according to the Common Terminology Criteria for Adverse Events (CTCAE), Version 5.0, Published: November 27, 2017.

Grading is based on the following general guideline:

- **Grade 1 Mild**; asymptomatic or mild symptoms; clinical or diagnostic observations only; intervention not indicated.
- **Grade 2 Moderate**; minimal, local, or non-invasive intervention indicated; limiting age-appropriate instrumental Activities of Daily Living (ADL).
- **Grade 3 Severe** or medically significant but not immediately life-threatening; hospitalization or prolongation of hospitalization indicated; disabling; limiting self-care ADL.
- Grade 4 Life-threatening consequences; urgent intervention indicated.
- Grade 5 Death related to AE.

AEs are coded using the Medical Dictionary for Regulatory Activities (MedDRA) version 22.0. The Clinical Data Management System (CDMS) auto-codes the majority of AEs to the latest version of the MedDRA dictionary. If this is not possible, AEs are coded from the MedDRA dictionary by the Cl.

SARs occurring from the first participant's dose of IMP to the last participant's end of follow-up are recorded on the trial MACRO database eCRF. Following this defined active monitoring period for SARs, investigators are still required to report any SARs or SUSARs which are brought to their attention.

For each SAE the following information is collected:

- 1. Full details in medical terms and case description
- 2. Event duration (start and end dates, if applicable)
- 3. Action taken
- 4. Outcome
- 5. Seriousness criteria
- 6. Causality in the opinion of the investigator

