5.1.1 Adverse events

The number of adverse events and adverse reactions (those possibly, probably or definitely related to treatment) and the worst grade AE and AR per participant will be summarised descriptively.

Example table: Number of events per participant

	Mean (SD)	Median (Q1, Q3)	Min, Max
All adverse events			
Adverse reactions (possibly, probably, definitely)			

Example table: Worst grade reported per participant (number, %)

	None	Mild	Moderate	Severe
All adverse events				
Adverse reactions (possibly, probably, definitely)				

The number of participants reporting each type of adverse event (by MedDRA System Organ Class) will be tabulated.

Example table: Number and percentage of participants affected by each adverse event, reported by System Organ Class

Event term		Total		Mild		Moderate		Severe	
	Ν	%	Ν	%	Ν	%	Ν	%	
Blood and lymphatic system disorders									
Cardiac disorders									
Endocrine disorders									
Eye disorders									
Gastrointestinal disorders									
General disorders and administration site conditions									
Immune system disorders									
Infections and infestations									
Injury, poisoning and procedural complications									
Investigations									
Metabolism and nutrition disorders									

The number and percentage of patients experiencing at least one high grade event (grade 3/4/5).

A line listing of all AEs will be reported, by participant, including severity, seriousness and relationship to study treatment.

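### The adverse-event tables do not separate untreated baseline time from time on carbamazepine, so all-cause percentages overstate on-drug experience and no off-drug summary is planned

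*SAP*

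**What the plan says.** SAP 4.2 defines a treated population, "Participants who have completed the baseline observation period and have received at least one dose of CBZ", but does not use it for safety. The same section says "Adverse events will be reported for all participants who start their baseline period".

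The collection window is set in SAP section 5: "All AEs occurring from the point of consent to the end of trial participation are recorded in the trial MACRO database eCRF". Protocol 10.2 sets the same window.

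SAP 5.1.1 then lists the summaries:

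- Counts per participant and worst grade, for all events and separately for "adverse reactions (those possibly, probably or definitely related to treatment) and the worst grade AE and AR per participant will be summarised descriptively".
- A table by organ class and severity, headed "Example table: Number and percentage of participants affected by each adverse event, reported by System Organ Class", with no column for relatedness.
- The number and percentage with at least one grade 3, 4 or 5 event.
- A line listing with severity, seriousness and relationship to treatment.

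SAP 5.1.2 adds SAE counts and an SAE listing. Only the SAE listing names an onset date. No table is split into baseline and treatment periods, restricted to events after first dose, or expressed per unit of exposure. No shell states its denominator.

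Elsewhere the plan does use the baseline period as a comparator. Protocol section 3 and SAP 1.1 say baseline data are there so that each child can be compared before and after treatment. The growth model (SAP 4.3.1) and the model for secondary outcomes (SAP 4.4.2) both carry a treatment-period indicator.

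**The concern.** Every child is observed off drug before treatment: 12 to 18 months in Stage 1 and 6 months in Stage 2. Events in that time cannot be caused by carbamazepine, yet they enter the same counts and percentages as events on drug. A reader of the final tables would take the organ-class and grade 3-5 percentages as a description of children on carbamazepine, and they would not be that.

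Surgery shows how this could happen. Operations for MCDS symptoms are recorded as adverse events (protocol 8.7.12, SAP 2.5), and the general guideline for grade 3 in SAP section 5 includes hospitalisation. An operation with an inpatient stay during baseline could therefore count in the grade 3-5 percentage before any drug was given.

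The protocol says that there are no previous studies of carbamazepine in MCDS and describes the second stage as assessing safety as well as efficacy (sections 2.3 and 5). The obvious safety question is whether events became more frequent on treatment. The planned tables do not address it, although the design supplies an off-drug period for every child.

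**Working it through.** The plan gives no event rate or safety calculation to reproduce. The check uses planned durations, then two illustrations that rest on stated assumptions.

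**Inputs.** Planned numbers are 11 + 29 = 40 (SAP 2.6). Baseline is 12 to 18 months in Stage 1 and 6 months in Stage 2 (SAP 2.4.1.1). Treatment is 24 months in Stage 1, with an optional further 12, and 12 months in Stage 2 (protocol summary).

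**Step 1: untreated share of observation.** All 40 children are assumed to follow the schedule. With b = Stage 1 baseline months and t = Stage 1 treatment months:

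- off drug = 11b + 29×6
- on drug = 11t + 29×12
- share = off / (off + on)

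| b | t | Off drug (person-months) | On drug (person-months) | Total (person-years) | Off-drug share |
|---|---|---|---|---|---|
| 12 | 24 | 306 | 612 | 76.5 | 33.3% |
| 12 | 36 | 306 | 744 | 87.5 | 29.1% |
| 18 | 24 | 372 | 612 | 82 | 37.8% |
| 18 | 36 | 372 | 744 | 93 | 33.3% |

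Untreated time is 306/12 = 25.5 to 372/12 = 31 person-years, of a total of 76.5 to 93. The 36-month rows are an upper bound on treatment time. Protocol 8.8.7 limits the extra year to eligible UK children who started before 2 March 2021, with all visits complete by 31 January 2024.

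**Step 2: direction and size for all-cause percentages.** For a child who is dosed, adding baseline time can add events but cannot remove any. The percentage of dosed children with at least one event can therefore only rise or stay the same, whatever the drug does.

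For size, assume a constant rate r per child-year, no drug effect, all 40 dosed, b = 12 and t = 24. Then P(at least one event) = 1 − exp(−r × years). At r = 0.25:

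- On drug: Stage 1 gives 1 − exp(−0.5) = 0.3935 and Stage 2 gives 1 − exp(−0.25) = 0.2212. The average is (11×0.3935 + 29×0.2212)/40 = 0.269.
- Pooled: Stage 1 gives 1 − exp(−0.75) = 0.5276 and Stage 2 gives 1 − exp(−0.375) = 0.3127. The average is (11×0.5276 + 29×0.3127)/40 = 0.372.

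So 27% on drug becomes 37% pooled. At r = 0.1 the change is 12% to 17%, and at r = 0.5 it is 46% to 60%. The rates are assumptions; the documents give none.

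**Step 3: adverse-reaction rows.** Pooling time does not lower these counts. The only route to understatement is a denominator that includes children never dosed. The displayed percentage is then the true one multiplied by dosed/40. Taking half of dosed children as having a reaction:

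| Never dosed (assumed, of 40) | Among dosed | As displayed |
|---|---|---|
| 0 | 20/40 = 50% | 20/40 = 50% |
| 2 | 19/38 = 50% | 19/40 = 47.5% |
| 4 | 18/36 = 50% | 18/40 = 45% |
| 8 | 16/32 = 50% | 16/40 = 40% |

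Protocol 7.2 and 8.4 provide for eligibility to be re-assessed after baseline and for withdrawal of children who fail, so never-dosed children are foreseen. Their number is not given.

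**The case against.** **Collection from consent is proper.** This stands. A reader might infer that counting baseline events breaches the protocol, because protocol 10.1 defines an adverse event as "Any untoward medical occurrence in a participant to whom a medicinal product has been administered". That reading fails: protocol 10.2 expressly requires recording from consent, and the SAP follows it. The point concerns tabulation, not collection.

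**The denominator is inferred.** This also stands. The sentence in SAP 4.2 is about coverage, the shells are labelled as examples, and none states an N. But nothing in the SAP assigns the treated population to any safety table, so the natural reading is everyone who starts baseline.

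**Safety is partly handled elsewhere.** Adverse reactions have their own rows for counts and worst grade, relationship is listed for each event, and SAEs carry an onset date. The independent data monitoring committee reviewed Stage 1 safety in eleven children, up to the last treated child's 6-month point (SAP 1.2). None of this puts a period split into the final tables, which cover all children and all later exposure.

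**An off-drug versus on-drug comparison is not like for like.** This stands and limits the remedy. Baseline visits are six months apart, and the Stage 1 6-month visit could be missed because of COVID-19. On drug there are three-monthly visits plus weekly calls during titration. Diaries run in both periods, but contact is denser on treatment, so the rate could rise through ascertainment alone.

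**Conclusion.** The concern holds in a limited form. The final tables mix off-drug and on-drug events, with about 29% to 38% of planned observation untreated. All-cause, organ-class and grade 3-5 percentages are inflated as a description of on-drug experience. The share of time rests on planned durations and full adherence to the schedule; the size of the inflation depends on event rates that the documents do not give.

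Two stronger readings are tempting, and the documents do not support them:

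- **That drug-related percentages are diluted.** This is conditional. It can affect only the adverse-reaction rows, and it is zero if every child who starts baseline is dosed. The untreated share of time does not measure it.
- **That the off-drug comparison is lost.** It is unplanned, not irrecoverable. Adverse events are scheduled for recording at baseline and treatment visits, so a split should be feasible if onset dates are held.

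This should be changed before the final tables are produced. It does not affect the primary growth analysis.

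**What to change.** 1. Tabulate adverse events, adverse reactions, SAEs and grade 3-5 events from first dose, among children with at least one dose.
2. Show baseline-period events (consent to first dose) in a separate column or table, for all who start baseline.
3. State the denominator in every table.
4. Give events per person-year by period, since planned baseline runs from 6 to 18 months and treatment from 12 to 36. Add a note that ascertainment is denser on treatment, so a higher on-drug rate is not by itself evidence of a drug effect.
5. Add onset date and period to the adverse-event line listing, and keep the listing for everyone.

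The cost is revised table shells and a split of event dates against first dose. No new data collection is needed, assuming the database holds onset dates for non-serious events; the SAP does not name that field, so this should be confirmed first.

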4.3 Primary analysis

The primary objective of Stage 2 is to evaluate efficacy of CBZ for the treatment of children with MCDS who are ambulant but have not yet reached skeletal maturity and to determine if the level of efficacy warrants a subsequent formal development programme for CBZ in this indication.

4.3.1 Statistical model for growth

For subject *i* (*i* = 1,..,*N*), let τ_{ij} be a treatment indicator taking the value 0 for measurements observed during the baseline period and 1 for measurements observed during the treatment period; treatment for individual *i* starts at time T_i .

Let y_{ij} denote a continuous response variable (e.g., height), observed at measurement times t_{ij} (j = 1,.., n_i), the model for which is:

$$y_{ij} = \beta_1 + \beta_2 t_{ij} + \beta_3 \tau_{ij} (t_{ij} - T_i) + \varepsilon_{ij},$$

where β_1 , β_2 and β_3 are regression parameters to be estimated using Generalised Estimating Equations (GEE). The "working" correlation matrix is given by,

$$Corr(\varepsilon_{ij}, \varepsilon_{ij'}) = \begin{cases} 1 & if \ j = j' \\ \rho & otherwise \end{cases}$$

This is sometimes referred to as an exchangeable covariance model. The first observation on each individual, y_{i1} , takes place at time t_{i1} =0.

- During the baseline period, $y_{ij} = \beta_1 + \beta_2 t_{ij} + \varepsilon_{ij}$.
- At the start of the treatment period, $y_{ij} = \beta_1 + \beta_2 T_i + \varepsilon_{ij}$.
- During the treatment period, $y_{ij} = (\beta_1 \beta_3 T_i) + (\beta_2 + \beta_3)t_{ij} + \varepsilon_{ij}$.

The parameter β_3 represents the change in slope between the baseline and treatment periods, i.e., the change in growth velocity.

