7.2 Exclusion Criteria

- Patients who have reached skeletal maturity*
- Patients who have a planned surgery or planned osteotomy (which in the opinion of the Chief Investigator, Principal Investigator and/or the clinical members of the TMG deems the patient unsuitable for the trial)**
- Patients who have had a prior adverse reaction to carbamazepine or similar drugs such as oxcarbazepine, or to any related tricyclic antidepressants.
- Patients known to have atrioventricular block
- Patients who have a history of bone marrow suppression/depression
- Patients who have evidence of chronic hepatic or renal impairment
- Patients who have acute intermittent porphyria
- Patients who have received a monoamine oxidase inhibitor within 14 days of commencing therapy
- Patients who have abnormal blood screening results at the time of treatment initiation will be excluded unless the Investigator believes the abnormality to be non-significant clinically
- Patients of Han Chinese, Thai and other Asian origins who carry the HLA-B*1502 allele

*Skeletal maturity will be assessed as part of the eligibility criteria. Individuals who may reach skeletal maturity before the end of the study should not be included. Patients will be assessed clinically on a case by case basis through discussion of the site PI^a with the CI and/or the clinical members of the TMG during the screening process.

If a participant reaches skeletal maturity during the treatment phase of the trial, they will be asked to continue on the trial for an additional 6 months from the point of skeletal maturity. Patients will stay on their medication and attend study visits, to evaluate if CBZ may have any effect on MCDS patients after they reach skeletal maturity.

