8.7.3 Tanner stage

Pubertal stage will be assessed by the clinician using validated Tanner staging criteria, in children aged 5 and older, at times specified in the schedule of events (Tables 5, 6, 7, 8 & 9) [Rasmussen et al 2015] (see Appendix 3). This is to evaluate the possibility that childbearing age has been reached in females and that pregnancy testing is therefore required during the trial (to be performed at the times specified in the schedule of events if indicated (Tables 5, 6, 7, 8 & 9). The Tanner staging criteria is also validated to use as a self-assessment [Morris et al 1980]. Self-assessment will be offered as an option, if participants prefer.

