8.7.7 Growth and Growth velocity

Growth will be recorded at times specified in the schedule of events (Tables 5, 6, 7, 8 & 9). The assessment to record growth will include:

- Total height (H) and length (L) if <2 years old
- Sitting height in children >=5 years old (SH)
- Crown-rump length (CRL) in children <5 years old
- Calculated sub ischial leg length (height/length sitting height/CRL)

All growth measurements will be recorded as described in Hall *et al* (Hall, Judith G. Handbook of normal physical measurements (2nd ed.), Oxford University Press, New York, 2007) and will be taken in triplicate to ensure accuracy.

Growth velocity will be measured by a change in annualised growth velocity from baseline based on measurements made in the 12-month(Stage 1)/6-month (Stage 2) observational phase (measured in cm/year).

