2.4.1.2.1 Alteration from baseline in height percentile over 12 months

Total height (length if age <2 years); sitting height (age \ge 5 years) and crown-rump length (age <5 years) are recorded at each baseline and treatment visit.

Height for age and sex, *zscores* are calculated using the ZANTHRO function in STATA; the "British 1990 Growth Reference" charts are used as the standard.

Vidmar, S. I., Cole, T. J., & Pan, H. (2013). Standardizing Anthropometric Measures in Children and Adolescents with Functions for Egen: Update. The Stata Journal, 13(2), 366–378. https://doi.org/10.1177/1536867X1301300211

2.4.1.2.2 Alteration from baseline in long bone alignment and configuration over 12 months as measured by X-ray analysis.

Using X-ray images of the hip and knees, bone alignment will be evaluated based on the angle formed between the head and neck of the femur and its shaft (Mikulicz angle), the femoral neck-shaft angle (NSA). To ensure consistency, the NSA will be assessed centrally by at least two independent radiologists to ensure consistency across sites. This will be measured according to the standards described in Keats TE Atlas of Roentenographic measurement Mosby 1990 p.289 p.320.

Outcome measures are:

- A. Bone age SD age related zscore (taken from the left wrist x-ray)
- B. Tanner and Whitehouse bone age (TW3)??
- C. Femoral neck-shaft angle (NSA) on left and right legs
- D. Deviation from midline at knee

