4.3.2 Analysis

All patients who have completed the baseline observation period and have received at least one dose of CBZ will be included in the primary analysis.

Height measurements will be displayed graphically by individual indicating measurements taken during baseline and treatment periods.

Height measurement data will be analysed using the STATA commend **xtgee** to estimate the parameters of the regression model in 4.3.1. The parameter β_3 representing the change in growth velocity will be reported together with 95% confidence interval. The Huber/White/sandwich estimator of variance will be used to obtain confidence intervals [in STATA: vce(robust)].

If fitting the growth model in section 4.3.1 is problematic, for example, lack of convergence, then a simplified analysis will be considered.

For subject *i* (*i* = 1,..,*N*), let v_{ik} denote growth velocity (a continuous response variable) measured during the baseline period (*k*=1) and the treatment period (*k*=2). Growth velocity during the baseline period for each participant will be estimated using the first available and last available measurement during the baseline period; the growth velocity during the treatment period will be estimated in a similar manner.

The model for growth velocity is:

$$v_{ik} = \beta_1 + \beta_{2i} + \beta_3 P_k + \varepsilon_{ik},$$

where β_1 , β_{2i} and β_3 are regression parameters to be estimated using simple linear regression. P_k takes the value 0 for baseline period velocities (*k*=1) and 1 for treatment period velocities (*k*=2). As for the previous GEE model, the parameter β_3 represents the change in growth velocity between treatment and baseline periods. The parameter β_3 representing the change in growth velocity will be reported together with 95% confidence interval.

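### β3 in cm/yr measures a treatment effect only if each child's untreated growth velocity stays constant with age, and no analysis of the primary outcome allows for change

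*SAP*

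**What the plan says.** The SAP's primary model (4.3.1) begins: "Let y_{ij} denote a continuous response variable (e.g., height), observed at measurement times". Its only regressors are time since the first visit and time since the start of treatment. Age, sex, pubertal stage and bone age do not enter. The coefficient β3 "represents the change in slope between the baseline and treatment periods, i.e., the change in growth velocity". Section 4.3.2 makes this the primary analysis and uses xtgee on the height measurements "to estimate the parameters of the regression model in 4.3.1". The SAP does not name the unit; Protocol 8.7.7 gives growth velocity in cm/year.

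The trial is single-arm and open-label. Eligibility sets no age limits beyond open epiphyses (Protocol 7.1). Length is recorded in children under 2 (8.7.7), and the consent rules cover patients of 16 and over (8.2). "Pubertal stage will be assessed by the clinician using validated Tanner staging criteria" from age 5 (8.7.3), but the stated purpose is pregnancy testing and the SAP does not use the result in any growth model.

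The other planned analyses of the primary outcome cover surgery and vitamin D (SAP 4.3.3) and prescribed dose (4.3.4). Age and sex are handled only in the secondary height outcome, where z-scores "are calculated using the ZANTHRO function in STATA" against the British 1990 reference (2.4.1.2.1). These are modelled with an added step at the start of treatment (4.4.2).

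**The concern.** Every child is older on treatment than at baseline. Without a concurrent control, a change in slope that comes from age cannot be told apart from one that comes from the drug. The cohort can run from toddlers to adolescents, so untreated velocity could move either way. If it slows, a real benefit is understated. If several children enter a pubertal spurt, an inactive drug can look effective. The confidence interval for β3 reflects sampling error and does not widen for this. Both documents state that the disease has no natural history studies, so constant velocity cannot be supported from MCDS data. β3 is the main estimate behind the question of whether to start a formal development programme.

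**Working it through.** The documents state no growth rate, effect size or standard deviation, so there is no figure of the plan's own to reproduce.

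**Inputs from the documents.** Stage 1: 11 children, baseline visits at 0, 6 and 12 months, then treatment visits every 3 months to 24 months, optionally 36. Stage 2: 29 children, baseline visits at 0 and 6 months, then every 3 months to 12 months (Protocol Table 4, SAP 2.5.1). The model and exchangeable working correlation are those of SAP 4.3.1.

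**Assumed.** Untreated velocity changes by a cm/yr per year of age, with a between 0.1 and 0.5 in size and negative for slowing. Data are complete, treatment starts at the last baseline visit, and no baseline is extended to 18 months.

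**Step 1. Bias of the planned model.** With no drug effect, height follows h(t) = h0 + v0·t + ½·a·t². The model fits the straight-line part exactly, and the curved part leaks into β3:

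β̂ = (Σ Xᵢ′R⁻¹Xᵢ)⁻¹ Σ Xᵢ′R⁻¹(½·a·tᵢ²), where Xᵢ has columns 1, t and max(0, t − Tᵢ).

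This gives β3 = k·a:

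| Treatment data used | k | Size of β3 for a = 0.1 to 0.5 (cm/yr) |
|---|---|---|
| First 12 months, all children | 0.67 | 0.07 to 0.34 |
| Stage 1 to 24 months | 1.57 | 0.16 to 0.79 |
| Six Stage 1 children to 36 months, five to 24 | 2.42 | 0.24 to 1.21 |
| All 11 Stage 1 children to 36 months | 2.71 | 0.27 to 1.36 |

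For ρ between 0.90 and 0.995, k moves by about 0.02 at most.

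**Step 2. The fallback in SAP 4.3.2.** A velocity taken from first to last height is the velocity at the midpoint of the period. The midpoint gap is 0.75 years in Stage 2 (1.00 − 0.25). In Stage 1 it is 1.0 year with 12 months of treatment (1.5 − 0.5) and 1.5 years with 24 months (2.0 − 0.5). The average is (29×0.75 + 11×1.0)/40 = 0.82, or (29×0.75 + 11×1.5)/40 = 0.96. The per-child term removes fixed differences between children but not this drift within a child.

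**Step 3. Effect on the confidence interval.** The planned GEE was simulated 200 times per scenario with Stage 1 data to 24 months. Assumptions: mean velocity 5 cm/yr, between-child velocity SD 0.8, measurement SD 0.3 cm. With no drug effect, the 95% interval (half-width about 0.25) excluded zero in 6% of runs at a = 0, 66% at a = ±0.2, 96% at a = −0.3 and 100% at a = ±0.5.

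**Step 4. With an assumed true effect of +1.0 cm/yr**, same follow-up, the model returned 0.21 at a = −0.5, 0.53 at a = −0.3 and 1.78 at a = +0.5. Subtracting the age-expected growth, taken as known, gave 1.00 each time.

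**Step 5. Would a covariate do?** With a = −0.5 and no drug effect, adding baseline age as a main effect left β3 at −0.78. A sex or baseline-age main effect shifts a child's level, not the bend in the growth curve.

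**Step 6. Puberty.** With an assumed 8 cm spurt on top of a = −0.3, mean β3 ran from −0.06 to −0.34 depending on the age mix, and the half-width rose to between 0.50 and 0.89. The two influences can partly cancel, so the net sign depends on who is enrolled.

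**The case against.** The strongest defence is that age is not ignored. SAP 4.4.2 already plans a change-in-slope model for the height z-score, and individual plots of height and z-score are planned too. That is real mitigation, but only in part. The analysis is secondary, and its step term can absorb some of the change that β3 should carry.

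A reader might infer that heights after skeletal maturity will flatten the treatment slope, because Protocol 7.2 says: "If a participant reaches skeletal maturity during the treatment phase of the trial, they will be asked to continue on the trial". The same footnote says that children who may mature before the study ends should not be enrolled, and eligibility is checked again before treatment. Such heights should be exceptions.

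A reader might also infer a bias above 1 cm/yr. In these calculations that needs the top of the assumed range and at least about half of Stage 1 continuing to 36 months. The extension is optional, needs fresh consent, is open only to children who started before 2 March 2021, and must end by 31 January 2024 (Protocol 8.8.7). For the stated 12-month endpoint the planned model's factor is 0.67.

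A third inference is that the z-score should replace the primary outcome. The documents do not support that. The protocol defines the outcome in cm/year and lists height percentile separately. The SAP is dated 08/02/2024, after the latest permitted last visit, in an open-label trial. The British reference describes the general population, while reported MCDS deficits mostly range from −7 to −3.6 SD (Protocol 2.1), so z-scores may themselves drift with age.

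Finally, no threshold on β3 triggers a decision. Efficacy is also judged on bone alignment, quality of life and pain, and the aim is to inform a later randomised trial. This lowers the stakes but does not make β3 interpretable alone.

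**Conclusion.** The concern holds. β3 in cm/yr cannot be attributed to carbamazepine alone, because nothing in the analysis of the primary outcome allows a child's untreated velocity to change with age. With no drug effect the expected β3 is about 0.67a at 12 months and 1.57a with Stage 1 data to 24 months, that is 0.07 to 0.34 and 0.16 to 0.79 cm/yr in size for a between 0.1 and 0.5. The factor reaches 2.7 only if all Stage 1 children complete 36 months. The multipliers follow from the visit schedule and the model; the values of a are assumptions. The direction is not fixed, so the bias cannot be called conservative. SAP 4.3.2 sets no 12-month cut-off, and 4.3.4 expressly keeps growth data from extended treatment. That enlarges the bias and departs from the 12-month endpoint. The remedy is a named companion analysis and a stated limitation, not a new primary outcome.

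**What to change.** In SAP 4.3.2 to 4.3.4:

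1. Add the 4.3.1 change-in-slope model, without the step term, fitted to the British 1990 height-for-age-and-sex z-score. Name it as an analysis of the primary outcome, report it beside the cm/yr β3, and base the efficacy conclusion on both.
2. Limit both fits to the first 12 months of treatment. This matches the stated endpoint and Protocol 8.8.7, which takes the Stage 1 endpoint at the end of dose titration (month 12 in Table 4). Show the longer Stage 1 data separately.
3. Repeat both in children who stay prepubertal: Tanner stage 1 throughout, or under 5 where staging is not done.
4. If any heights were taken after skeletal maturity, give results with and without those children. Dropping only their treatment-period heights would remove the slowest growth from one side and push β3 upward.
5. State the constant-velocity assumption, and that β3 in cm/yr is not attributable to the drug alone.

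The cost is SAP wording and a few extra model fits on data already collected or derived. The change should be dated and declared as made before the final analysis. Some age drift can remain because the reference is for the general population, and the prepubertal subset will be smaller and less precise.
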